#### Analysis of the Primary Efficacy Endpoint:

Analysis of the primary efficacy endpoint will be performed using Cochran-Mantel-Haenszel (CMH) test stratified by concomitant steroid use at Baseline ( $\geq 20$  vs.  $< 20$  mg daily), and screening hemoglobin level ( $< 9$  vs.  $\geq 9$  g/dL). The odds ratio will be presented along with the 95% CI. The study will be considered to meet its primary efficacy objective if the lower bound of the 95% CI of odds ratio of durable hemoglobin response between the Fostamatinib and Placebo treated subjects is greater than 1.

In addition, the exact Clopper-Pearson 95% CI for the proportions and the Agresti-Min exact unconditional CI for the difference in proportions will be estimated.

The difference in proportion of durable hemoglobin response between the two treatment groups will be estimated and the 95% Miettinen-Nurminen score CIs will be computed taking into account the stratification factors.

Sensitivity analysis for primary endpoint will be evaluated using subgroup prognostic, multiple imputation for missing data, and a washout of 6 weeks for rescue treatment exclusion period.

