## 10.0 DATA ANALYSIS AND STATISTICAL METHODS

This section provides the key details of the statistical analyses to be performed using data captured according to this protocol. A complete statistical analysis plan (SAP) describing all planned analyses will be finalized prior to database lock.

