#### Sample Size for Primary Endpoint: Achievement of durable hemoglobin response

In a previous phase 2 study, the efficacy of 12 to 24 weeks of treatment with fostamatinib in subjects with wAIHA who had failed at least one prior treatment regimen was evaluated. Approximately 27% (7 out of 26) of subjects treated with fostamatinib achieved a durable response, defined as a hemoglobin level above 10 g/dL with at least 2 g/dL higher than the baseline hemoglobin, not attributable to RBC transfusion or other rescue treatments on at least 3 scheduled visits within 24 weeks of treatment. No data are available on placebo response rates for this population. It is expected that no more than approximately 5% of placebo subjects would achieve a durable hemoglobin response.

Under these assumptions, a sample size of 90 subjects (i.e., 45 subjects per treatment group) will yield at least 84% power to detect a difference between the 2 groups at the 0.05 two-sided significance level using Fisher's exact test.

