### **10.3.3 Demographic and Baseline Characteristics**

Baseline and demographic characteristics such as age, weight (kg), height (cm), body mass index (kg/m^2), ethnicity, race, sex, disease type (i.e., primary or secondary), duration of AIHA, Baseline corticosteroid use (Yes/No), number of unique prior AIHA therapies, prior AIHA therapies, splenectomy (Yes/No), rituximab (Yes/No), hemoglobin (g/dL), LDH (U/L), reticulocyte (10^9/L), and haptoglobin (g/L), at Baseline will be summarized by treatment group for the ITT population.

For continuous variables, number of observations, mean, median, standard deviation, minimum and maximum values, and 25th and 75th percentiles will be presented. For categorical variables, counts, and percentages will be tabulated for each category.

All randomly assigned subjects will be included in the analysis. Missing values will not be imputed.

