### **10.3.6 Analysis of Primary Efficacy Endpoint**

The primary efficacy endpoint is achievement of durable hemoglobin response (Yes/No) defined as achieving a hemoglobin level  $\geq 10$  g/dL with an increase from Baseline in hemoglobin level of  $\geq 2$  g/dL on 3 consecutive available visits during the 24-week treatment period, in which hemoglobin measurements eligible for this definition occurred outside a Rescue Treatment Visit Exclusion Period.

Available visits are defined as any scheduled visit where a plasma sample was collected, and hemoglobin level analyzed using either central or local laboratory.

For permitted rescue medications, a Rescue Treatment Visit Exclusion Period begins with the initiation of the rescue medication. The end of a Rescue Treatment Visit Exclusion Period is 4 weeks (28 days) following the return of steroid use to Baseline level or the last administration of rescue medication, whichever event occurs the latest. Any hemoglobin measurements made during this exclusion period are not eligible for any endpoint definition.

For non-permitted rescue medications, a Rescue Treatment Visit Exclusion Period begins with the initiation of the rescue medication and ends at Week 24/Week 26 or date of early termination from study.

If durable hemoglobin response cannot be determined because the subject discontinued from the study prior to attaining a durable response, then the subject will be assumed as not having achieved a durable response.

Analysis will be performed after all randomized subjects have completed the 24 weeks of treatment or discontinued from the study. All subjects randomized will be included in the analysis (ITT population). The following hypothesis will be evaluated:

$$H_0: \Theta_{\text{Fostamatinib,Placebo}} = 1$$

$$H_a: \Theta_{\text{Fostamatinib,Placebo}} \neq 1,$$

where  $\Theta_{\text{Fostamatinib,Placebo}}$  is the odds ratio of durable hemoglobin response due to treatment.

Analysis will be performed using Cochran-Mantel-Haenszel (CMH) test stratified by concomitant steroid use at Baseline ( $\geq 20$  vs.  $< 20$  mg daily), and screening hemoglobin level ( $< 9$  vs.  $\geq 9$  g/dL). The odds ratio will be presented along with the 95% CI. The study will be considered to meet its primary efficacy objective if the lower bound of the 95% CI of the odds ratio of durable hemoglobin response between the Fostamatinib and Placebo-treated subjects is greater than 1.

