In addition, the exact Clopper-Pearson 95% CI for the proportions and the Agresti-Min exact unconditional CI for the difference in proportions will be estimated.

The difference in proportion of durable hemoglobin response between the two treatment groups will be estimated and the 95% Miettinen-Nurminen score CIs will be computed taking into account the stratification factors.

A variety of sensitivity analyses of the primary analysis will be performed. These sensitivity analyses will consider:

- adjusting for prognostic variables for which an imbalance existed between the treatment groups at Baseline
- durable hemoglobin response derived using the hemoglobin values imputed
- changing the 4-week washout period in a Rescue Treatment Visit Exclusion Period to a 6-week washout period

Details will be provided in the SAP.

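### The covariate-adjusted sensitivity analysis of the primary endpoint chooses its covariates by observed Baseline imbalance, so its final model cannot be known before unblinding; the primary test is not affected

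*Combined protocol and SAP*

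**What the plan says.** The primary analysis in Section 10.3.6 is fully named: "Analysis will be performed using Cochran-Mantel-Haenszel (CMH) test stratified by concomitant steroid use at Baseline" (cut at 20 mg daily) and by screening hemoglobin (cut at 9 g/dL). Success is judged on the lower 95% confidence limit of the odds ratio.

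The same section then states: "A variety of sensitivity analyses of the primary analysis will be performed". The first of three items is "adjusting for prognostic variables for which an imbalance existed between the treatment groups at Baseline". The other two concern imputed hemoglobin values and a longer washout after rescue. The list closes with "Details will be provided in the SAP", and Section 10.0 promises a SAP "describing all planned analyses will be finalized prior to database lock". The combined document contains no separate SAP text that names candidate variables, a measure or threshold of imbalance, or a model.

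The synopsis describes the analysis differently: "Sensitivity analysis for primary endpoint will be evaluated using subgroup prognostic", followed by multiple imputation and the 6-week washout. It mentions no imbalance rule.

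Section 10.3.3 lists Baseline characteristics for description and designates none of them for adjustment. By contrast, the FACIT-F model in Section 10.3.7 names the Baseline score as a covariate without any condition on balance.

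**The concern.** Under 1:1 stratified randomization, a Baseline difference between arms is due to chance. A covariate is worth adjusting for because it predicts the outcome, whether or not the arms differ on it. A rule triggered by imbalance has two drawbacks:

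- The model depends on unblinded data. Different reasonable definitions of imbalance can give different models, and a reader cannot tell whether the one reported was the one intended.
- A strong predictor is ignored whenever it happens to be balanced, so the precision it could add is lost.

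What is at stake is the value of this analysis as evidence that the primary result is robust.

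**Working it through.** **1. Can the SAP close the gap?** The SAP is due before database lock (Section 10.0). Sections 5.7 and 10.3 place unblinding after lock. Imbalance by arm is visible only after unblinding. A SAP could therefore fix the candidates, the measure and the threshold. While the imbalance condition stands, it could not fix the final model.

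**2. Can a plausible predictor be missed?** Response needs hemoglobin of at least 10 g/dL and a rise of at least 2 g/dL, so the rise required is max(2, 10 − Baseline): 3 g/dL from a Baseline of 7, and 2 g/dL from 8 or above. Randomization is stratified on screening hemoglobin at 9 g/dL, which tends to balance hemoglobin between arms. An imbalance trigger is then less likely to select it, and the stratified test uses it only as a dichotomy.

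**3. Design inputs and the plan's own power figure.** Section 10.1 gives 45 per arm, 27% vs 5%, and a "difference between the 2 groups at the 0.05 two-sided significance level", with at least 84% power by Fisher's exact test. Summing Bin(i; 45, 0.27) × Bin(j; 45, 0.05) over all tables with two-sided Fisher p ≤ 0.05 gives 78.0%, so 84% is not reproduced with the named test. That is a separate matter. The simulations below use score or likelihood-ratio tests. The exact power of the Pearson test at these inputs is 86.6%, which agrees with the simulated unadjusted values.

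**4. Power with one covariate.** The documents give no prognostic strength, so the log odds ratio b per SD is an assumption, shown as a range. There were 20,000 simulated trials per row, with one standard-normal covariate, marginal rates held at 27% and 5%, and score tests. The simulation error of one power value is about √(0.87 × 0.13 / 20,000) = 0.24 points. Two decimals are shown only so that the differences can be checked.

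| b (odds ratio per SD) | Unadjusted | Adjust only if imbalance p<0.10 | Always adjust | Always minus trigger |
|---|---|---|---|---|
| 0 (1.0) | 86.41% | 86.14% | 85.45% | −0.69 |
| 0.5 (1.6) | 86.70% | 86.62% | 86.61% | −0.01 |
| 1.0 (2.7) | 86.70% | 87.08% | 89.30% | +2.22 |
| 1.5 (4.5) | 86.66% | 87.56% | 91.98% | +4.42 |
| 2.0 (7.4) | 86.09% | 87.69% | 94.58% | +6.89 |

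The trigger selects the covariate in only about 10% of trials, so its power stays close to the unadjusted test. A useless covariate costs 86.41 − 85.45 = 0.96 points against no adjustment.

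**5. Power with two covariates.** With only two prognostic covariates eligible (4,000 trials per setting, likelihood-ratio tests), always adjusting gave 87.1% against 86.2–86.4% without fixed adjustment at b = 0.3 each, 88.5% against 86.6% at b = 0.5, and 89.8% against 86.4–86.9% at b = 0.7 (odds ratio 2.0). The gains are about 1, 2 and 3 points.

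**6. Type I error.** With both arms at 16%, a fixed p<0.10 trigger rejected in 4.4–5.2% of trials, so it does not inflate the error. An open choice is different. With five candidates, reporting the most favorable of the unadjusted and the permitted single-covariate results raised the favorable-direction error of this analysis from about 2.5–2.7% to 2.9–3.9%, depending on the imbalance cut used.

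**7. How large a model?** Expected responders are 45 × 0.27 + 45 × 0.05 = 12.15 + 2.25 = 14.4. Treatment, two stratification factors and one or two covariates make four or five coefficients, which is 14.4/4 = 3.6 or 14.4/5 = 2.9 responders each. That is why the set must be small and the fit penalized.

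**The case against.** Whether a chance imbalance in a known prognostic factor could explain the result is a fair robustness question. The rule is also limited to prognostic variables, and the SAP could list candidates and a threshold before anyone sees treatment codes. Most of this stands. Such a SAP would remove the open choice in step 6. It would not remove the dependence on observed balance in step 1, nor the omission of balanced predictors.

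The simulations simplify the plan. Their reference is an unadjusted test, whereas the primary analysis already stratifies on two factors. Continuous Baseline hemoglobin overlaps one of those factors, so its added information is probably smaller than that of an independent covariate. The documents also do not show that disease type predicts response. These objections stand and are reasons to read the power figures as a range.

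A reader might treat every characteristic in Section 10.3.3 as a candidate and infer that some imbalance is more likely than not. The text does not support that. The rule covers prognostic variables only, and several listed items overlap or relate to the stratification factors. With two to five independent prognostic candidates (an assumption) tested at 0.05, the chance of at least one imbalance is 1 − 0.95² = 10% to 1 − 0.95⁵ = 23%. A reader might also take the synopsis as stating the same rule. It does not, and its wording could equally mean a subgroup analysis.

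**Conclusion.** The point holds as a minor one. Section 10.3.6 states a selection rule, so this is a weaker method than naming the covariates and not just detail left for later. The main loss is credibility as a robustness check. Lost power is secondary and is material only if a covariate is strongly prognostic, which the documents neither show nor exclude.

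A reader might infer that the trial's conclusion or its error control is at risk. The documents do not support this. Success rests on the pre-specified stratified test, and under Section 10.4 the testing of secondary endpoints depends on that result alone. No trial decision uses the power of this sensitivity analysis.

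**What to change.** Replace the first sensitivity item in Section 10.3.6 with text along these lines: *Durable response will also be analyzed by Firth-penalized logistic regression with treatment, the two stratification factors, continuous Baseline hemoglobin and disease type (primary or secondary); these covariates are fixed before unblinding and used regardless of observed balance.*

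The two covariates are examples. The sponsor should name one or two on prognostic grounds and no more, given the expected number of responders. Align the synopsis so that it describes the same analysis. An imbalance-based adjustment may be kept if it is labelled exploratory.

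The cost is a sentence in the protocol and SAP and the matching synopsis edit. Both example covariates are already in Section 10.3.3, so no new data are needed. The downside is the loss of about 1 point of power in this supportive analysis if a chosen covariate proves non-prognostic.

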### 10.3.7 Analysis of Secondary Efficacy Endpoints

The secondary endpoints for this study are: hemoglobin response on at least one visit (Yes/No), achievement of change from Baseline in hemoglobin level  $\geq 2$  g/dL (Yes/No), change in hemoglobin values from Baseline to End of Treatment (Week 14 to Week 24), the use of permitted rescue medications after Week 4 (Yes/No), and change from Baseline to Week 24 in Functional Assessment of Chronic Illness Therapy - Fatigue scale (FACIT-F).

Adjustment for multiple testing using the hierarchical method as described in [Section 10.4](#).

The proportion of subjects who achieve hemoglobin response on at least one visit, proportion of subjects who achieve a change from Baseline in hemoglobin level  $\geq 2$  g/dL, and proportion of subjects using permitted rescue medications after Week 4 will be summarized. All subjects randomized will be included in the analysis (ITT population). Subjects with no assessment for hemoglobin response will be treated as non-responders. Subjects with no assessment for change from Baseline in hemoglobin level will be treated as failure to achieve a change from Baseline in hemoglobin level  $\geq 2$  g/dL.

Analysis of hemoglobin response on at least one visit, change from baseline in hemoglobin level  $\geq 2$  g/dL, and use of rescue medications after Week 4 will be performed using the CMH test stratified by concomitant steroid use at Baseline ( $\geq 20$  vs.  $< 20$  mg daily), and Screening hemoglobin level  $< 9$  vs.  $\geq 9$  g/dL). In addition, the exact Clopper-Pearson 95% CI for the overall proportions will be estimated by treatment group. In addition, the Agresti-Min exact unconditional 95% CI for the difference in proportions will be estimated as well as the 95% Miettinen-Nurminen score CIs  taking into account the stratification factors.

Change in hemoglobin value from Baseline to End of Treatment (Week 14 to Week 24) will be summarized using descriptive statistics, such as mean, standard deviation, and 95% CI. For each of the 200 imputed datasets in each imputation setting, change from Baseline to End of Treatment in hemoglobin levels will be analyzed using an analysis of variance (ANOVA) model with concomitant steroid use at Baseline ( $\geq 20$  vs.  $< 20$  mg daily), Screening hemoglobin level ( $< 9$  vs.  $\geq 9$  g/dL) and treatment group as fixed effect in the model. Least squares mean with the 95% CI for the mean will be constructed for each treatment group and for the differences between the treatment groups. Rubin's rules will be implemented to combine the results from all imputed datasets to provide the overall p-value, 95% CI, and difference between the treatment groups.

The overall FACIT-F score (defined in [Section 4.3](#)) prorated for missing items will be calculated, and the change from Baseline in overall score will be summarized for each treatment group at Baseline, Week 12, and Week 24. The number of observations, mean, median, standard deviation, and minimum and maximum values, 25th and 75th percentiles, and 95% CIs will be presented. In addition, box plots will be presented by treatment group for both raw values and for change from Baseline to Weeks 12 and 24. Change from Baseline to Week 12 and Week 24 in the FACIT-F will be analyzed using Mixed effect model for repeated measures implemented by SAS PROC MIXED. The model will use change from Baseline in FACIT-F as a response variable and include the fixed categorical effects of treatment group, weeks (12 and 24),

interaction between treatment and weeks, concomitant steroid use at Baseline ( $\geq 20$  vs.  $< 20$  mg daily), Screening hemoglobin level ( $< 9$  vs.  $\geq 9$  g/dL), and Baseline FACIT-F as a covariate.

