#### Analysis of Secondary Efficacy Endpoints:

Analysis of binary secondary efficacy endpoints (hemoglobin response on at least one visit, achievement of a change from Baseline in hemoglobin level of 2 g/dL or greater, use of permitted rescue medications after Week 4) will be performed using the CMH test stratified by concomitant steroid use at Baseline ( $\geq 20$  vs.  $< 20$  mg daily), and Screening hemoglobin level  $< 9$  vs.  $\geq 9$  g/dL). In addition, the exact Clopper-Pearson 95% CI for the overall proportions will be estimated by treatment group. In addition, the Agresti-Min exact unconditional 95% CI for the difference in proportions will be estimated as well as the 95% Miettinen-Nurminen score CIs taking into account the stratification factors.

Change from Baseline to End of Treatment in hemoglobin levels will be analyzed using an analysis of variance (ANOVA) model with multiple imputations with concomitant steroid use at Baseline ( $\geq 20$  vs.  $< 20$  mg daily), screening hemoglobin level ( $< 9$  vs.  $\geq 9$  g/dL) and treatment group as fixed effect in the model. The missing hemoglobin values will be imputed. Least squares mean with the 95% CI for the mean will be constructed for each treatment group and for the differences between the treatment groups.

Change from Baseline to Week 12 and Week 24 in the FACIT-F will be analyzed using Mixed effect model for repeated measures implemented by SAS PROC MIXED. The model will use change from Baseline in FACIT-F as a response variable and include the fixed categorical effects of treatment group, weeks (12 and 24), interaction between treatment and weeks, concomitant steroid use at Baseline ( $\geq 20$  vs.  $< 20$  mg daily), Screening hemoglobin level ( $< 9$  vs.  $\geq 9$  g/dL), and Baseline FACIT-F as a covariate.

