#### 4.3 Secondary Efficacy Endpoints

The secondary efficacy endpoints within the 24 weeks of treatment are:

1. Hemoglobin response on at least one visit (Yes/No)
2. Achievement of a change from Baseline in hemoglobin level of 2 g/dL or greater (Yes/No)
3. Change in hemoglobin value from Baseline to End of Treatment (Week 14 to Week 24)
4. Use of permitted rescue medications after Week 4 (Yes/No)
5. Change from Baseline to Week 24 in Functional Assessment of Chronic Illness Therapy - Fatigue scale (FACIT-F)

End of Treatment hemoglobin is defined as the mean of the hemoglobin values from the last 6 available visits between Week 14 and Week 24, inclusive, as long as those visits occurred outside a Rescue Treatment Visit Exclusion Period.

The FACIT-F scale is a short, 13-item, easy to administer tool that measures an individual's level of fatigue during their usual daily activities over the past week. Each item is rated using a 5-point Likert-type scale (0 = not at all; 1 = a little bit; 2 = somewhat; 3 = quite a bit; and 4 = very much). Negatively stated items are reversed by subtracting the response from "4". After reversing proper items, all subscale items are summed to a total, which is the subscale score. All items contribute to the sum score with equal weight. The scale range is 0 to 52, with 0 being the worst possible score and 52 being the best possible score indicating no fatigue (see FACIT

Administration and Scoring Guidelines, and Cella 2002). The overall score will be calculated and prorated for missing items as follows:

$$\text{Total Score} = [\text{Sum of item scores}] \times [\text{N of items in subscale}] \div [\text{N of items answered}]$$

The FACIT-F change scores will be computed as (Week 24 score - Baseline score).

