## 7.2 Baseline/Day 1/First Dose (Day 1/Week 0)

The Baseline/First Dose visit will occur within 28 days after screening.

To be eligible for enrollment in the study, subjects must have met all inclusion/exclusion criteria at the baseline visit prior to first dose.

The Medical Monitor must review and approve each subject's eligibility verification form prior to randomization.

The following assessments will be completed prior to study drug administration:

- Changes in medical history
- FACIT-F and EQ-5D Questionnaires: Subject is to read questionnaire by him/herself and write/mark answers directly onto the questionnaire
- Abbreviated physical examination
- Concomitant Medications
- Vital Signs (blood pressure, pulse, and temperature)
- Hemoglobin level and reticulocyte count
- CBC, differential, and platelet count
- Serum Chemistry (with LFTs)
- Haptoglobin
- XXXXXXXXXX (see [Section 7.13.7](#))

---

 NOTE: If the initial blood pressure at any visit is  $\geq 130$  mmHg systolic or  $\geq 80$  mmHg diastolic, the subject should remain seated and the blood pressure should be taken at least 2 additional times at least 3 minutes apart. If the average of the 3 measurements is  $\geq 130$  mmHg systolic or  $\geq 80$  mmHg diastolic, follow the guidelines in [Appendix 2](#).

- Urinalysis
- Serum pregnancy test (for females of childbearing potential)
- Randomize for drug assignment in RTSM system

All subjects start the study at the 100mg dose. The first dose of study drug should be administered in the clinic to ensure that the subject understands dosing instructions. For all subjects, this dose will be considered the evening dose for this day no matter what time it is administered. Study staff will instruct the subject to take the study drug *bid* beginning the following morning. See [Section 8.4](#) for additional information regarding study drug dispensation and administration.

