## **10.4 Multiple Comparisons/Multiplicity**

Analysis of secondary endpoints will be performed only if the primary efficacy analysis is significant at the 0.05 level using the gatekeeping procedure. Secondary efficacy analyses and secondary outcomes will be used to assess the consistency of the primary efficacy analysis.

Adjustment for multiple testing will be performed using the hierarchical approach to control the overall Type I error for the study. If the primary efficacy endpoint is statistically significant, 5 secondary endpoints will be tested sequentially in the order as listed in [Section 4.3](#) with the corresponding p-values of  $p_1$ ,  $p_2$ ,  $p_3$ ,  $p_4$  and  $p_5$ , respectively. Given  $\alpha=0.05$ , at any time if  $p_i > \alpha$ ,  $i=1,2,3,4,5$ , testing will be stopped with no statistically significant differences for the  $i^{\text{th}}$  and later secondary endpoints. If testing continues to  $p_5 < \alpha$ , all 5 endpoints will be considered statistically significant.

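### The hemoglobin-change ANOVA omits Day 1 hemoglobin as a covariate; it is valid as planned, but one added term may sharpen the estimate and its CI

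*Combined protocol and SAP*

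**What the plan says.** Section 10.3.7 fits the same model in each of 200 imputed datasets and pools the results by Rubin's rules: "change from Baseline to End of Treatment in hemoglobin levels will be analyzed using an analysis of variance (ANOVA) model with concomitant steroid use". The other terms are screening hemoglobin in two levels (below 9 versus 9 g/dL or more) "and treatment group as fixed effect in the model". The synopsis agrees: "Change from Baseline to End of Treatment in hemoglobin levels will be analyzed using an analysis of variance (ANOVA) model", with the same terms. Neither place includes continuous Baseline hemoglobin.

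The value is available. Section 7.2 lists "Hemoglobin level and reticulocyte count" among the assessments made before study drug. The screening value behind the stratum can be several weeks older: "The Baseline/First Dose visit will occur within 28 days after screening". The outcome itself is averaged over visits. Section 4.3 says "End of Treatment hemoglobin is defined as the mean of the hemoglobin values from the last 6 available visits" from Week 14 to Week 24, outside rescue exclusion periods.

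For the other continuous change endpoint, FACIT-F, the model in section 10.3.7 has the same two strata and also the outcome's own baseline score.

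Section 10.4 sets the order of testing: "Analysis of secondary endpoints will be performed only if the primary efficacy analysis is significant at the 0.05 level using the gatekeeping procedure". The five secondary endpoints then follow in a fixed sequence at 0.05, with hemoglobin change third.

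**The concern.** Change is End of Treatment minus Baseline. Unless the slope of End of Treatment on Day 1 hemoglobin is 1, the change score stays correlated with Baseline. Any chance difference in Day 1 hemoglobin between arms then enters the treatment estimate multiplied by (slope − 1), and Baseline variation adds to the residual variance. A single Day 1 reading set against a mean of up to six visits tends to pull the slope below 1, although a wider spread at End of Treatment can offset this.

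The screening stratum corrects only part of it, because it has two levels and may come from a sample taken up to 28 days earlier. At stake are the width of the reported CI and how far one trial's estimate can be moved by chance imbalance. Average bias and the error rate are not at stake. The plan gives no reason for adjusting FACIT-F for its own baseline while leaving hemoglobin unadjusted.

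**Working it through.** The documents state no power, SD, correlation or effect size for this endpoint, so there is no figure of the plan's own to reproduce. From the documents: n = 90 allocated 1:1, the strata, the eligibility limit of hemoglobin below 10 g/dL at screening, and durable response rates of 27% versus 5% (section 10.1). Assumed: End of Treatment SD 1.8 g/dL, Baseline SD 0.9 to 1.3 with mean 8.3, and screening-to-Day 1 correlation 0.6 to 0.8. These SDs and correlations apply before the eligibility cut.

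**1. Formula.** Let *b* be the slope of End of Treatment on Day 1 hemoglobin, *V* the variance of Day 1 hemoglobin within strata, and *s²* the variance of End of Treatment given Day 1.

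- Residual variance, planned ANOVA: (1 − b)²V + s²
- Residual variance with the covariate: s²
- Variance ratio: s² / [(1 − b)²V + s²] × 86/85 (error degrees of freedom 90 − 4 and 90 − 5)
- SD of the Day 1 imbalance left after the strata: √(4V/90)
- Shift in the planned estimate from a 1-SD imbalance: |b − 1| × that SD

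**2. Worked case.** Baseline SD 1.1, with the stratum explaining 20% of Day 1 variance: V = 1.21 × 0.80 = 0.968. The imbalance SD is √(4 × 0.968/90) = 0.21 g/dL. With correlation r, b = r × 1.8/1.1 and s² = 3.24 × (1 − r²).

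| r | b | (1 − b)²V | s² | Variance ratio | 1-SD shift (g/dL) |
|---|---|---|---|---|---|
| 0 | 0 | 0.968 | 3.240 | 0.78 | 0.21 |
| 0.3 | 0.49 | 0.251 | 2.948 | 0.93 | 0.11 |
| 0.5 | 0.82 | 0.032 | 2.430 | 1.00 | 0.04 |
| 0.7 | 1.15 | 0.020 | 1.652 | 1.00 | 0.03 |

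**3. Full range.** A large-sample calculation (500,000 subjects per cell, screening hemoglobin below 10, stratum cut at 9) gives these variance ratios, with covariate over without:

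| Baseline SD | r = 0 | r = 0.3 | r = 0.5 | r = 0.7 |
|---|---|---|---|---|
| 0.9 | 0.84–0.87 | 0.98 | 1.01 | 0.95–0.96 |
| 1.1 | 0.78–0.82 | 0.93–0.95 | 1.00 | 1.00 |
| 1.3 | 0.72–0.77 | 0.88–0.90 | 0.96–0.97 | 1.01 |

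CI width changes by the square root: √0.88 = 0.94 and √0.98 = 0.99 at r = 0.3. The stratum explains 13% to 28% of Day 1 variance. The imbalance left has SD 0.15 to 0.24 g/dL, and a 1-SD imbalance moves the estimate by 0.06 to 0.14 g/dL at r = 0.3 and by 0 to 0.08 at r = 0.5.

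Section 7.2 also says "To be eligible for enrollment in the study, subjects must have met all inclusion/exclusion criteria at the baseline visit prior to first dose". If that means Day 1 hemoglobin must be below 10 as well, the variance changes are −24% to −13%, −10% to −2%, −3% to +1% and −4% to +1% at r = 0, 0.3, 0.5 and 0.7. If screening and Day 1 hemoglobin are equally correlated with End of Treatment, the ratios are 0.85–0.97 at 0.3 and 0.91–1.01 at 0.5.

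**4. A second set of assumptions.** Trials of 45 per arm were simulated with Baseline SD 1.0 to 1.3, End of Treatment SD 1.5 to 2.0, correlation 0.2 to 0.7 and a true difference of 1.0 g/dL. The standard error changed by −11% to about +0.5%. Power for this test taken alone changed by about −1 to +8 points. The largest gain (SDs 1.3 and 1.5, correlation 0.2) took the standard error from 0.351 to 0.312 and power from 81% to 89%.

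**5. Within the hierarchy.** Trials were simulated with 12 visits, stratified CMH tests for the primary and first two secondary endpoints, and durable response set near 27% versus 5%. The gates were passed in 55% to 84% of trials. Among those, the planned ANOVA was significant in 92% to 100%. The covariate changed the chance of passing the gates and this test by −0.1 to +1.2 points at r = 0.3, by −0.3 to +0.6 at r = 0.5, and by at most 2.7 points anywhere (r = 0, Baseline SD 1.3).

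**6. Validity.** In 6,000 null trials, type I error was 0.049–0.054 for the planned ANOVA and 0.047–0.053 with the covariate. With a true difference of 1.0, mean estimates were 0.98 to 1.02 for both models.

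**The case against.** The planned ANOVA is valid and adjusts for exactly the factors used in randomization, which is an accepted choice. The gain is not guaranteed: it disappears when the slope is near 1, which under these assumptions means correlations of about 0.5 to 0.7. The largest gains need a correlation of 0 between a subject's own Baseline and End of Treatment values. No decision is likely to change, because trials that reach this test nearly always pass it. All of this stands, and it is why the point ranks low.

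Three limits on the figures also stand. First, the stated SDs and correlations are values before the eligibility cut. After it, the Baseline SD is about 0.86 to 1.23 (0.83 to 1.10 if Day 1 is also limited), and a nominal correlation of 0.3 becomes 0.25 to 0.29. Second, the simulations used complete data, whereas the plan uses multiple imputation and drops visits in rescue exclusion periods, so the gain under the planned imputation is unknown. Third, section 10.6 leaves missing-data handling to SAP detail not in the text reviewed, so whether the imputation model uses Baseline hemoglobin could not be checked.

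None of these removes the asymmetry between a loss of about 1% in variance at worst and a plausible gain of several percent.

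**Conclusion.** The point holds as a low-priority improvement. The term list leaves out a baseline value that the trial already collects, while the FACIT-F model includes its own. The planned result would be neither biased on average nor wrong in its error rate.

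At a Baseline to End of Treatment correlation of 0.3, the expected benefit is a 2% to 12% smaller variance, together with removal of shifts of about 0.1 g/dL from a typical chance imbalance. At 0.5 or above, the variance change lies between a 5% fall and a 1% rise. These figures depend on the assumed SDs and correlations and on complete data; confidence in the size is medium. The primary conclusion is unaffected, and nothing here indicates that the fourth and fifth secondary endpoints are at risk.

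**What to change.** Before unblinding, add continuous Day 1 Baseline hemoglobin as a covariate to the hemoglobin-change model in section 10.3.7 and the synopsis. Keep both strata and treatment, fit the model in each imputed dataset, and pool by Rubin's rules as already planned.

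The cost is one model term, one degree of freedom, and matching edits in both places and in the SAP. No new data are needed. Under the full-range assumptions above, the worst case is about 1% more variance, or a CI about 0.6% wider. The term should be specified in advance, because adding it after an imbalance has been seen would invite criticism.
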